6.4.3.9 Breaking time of the tear film

One of the first aspects of the tear film that changes when there is an alteration to the ocular surface, is its stability. In general, if the corneal or conjunctival surface is damaged, it is unlikely that a stable tear film can be maintained.

The most common method to evaluate the stability of the tear film is the evaluation of TRL with fluorescein. Once the fluorescein is instilled, with the cobalt blue filter the patient is asked not to blink. The precorneal colored fluorescein layer will change to less fluorescent or non-fluorescent regions. The time that elapses from the last blink until the appearance of these regions is the TRL. It will be reported in seconds, in the clinical file and in the CRF.

6.4.3.10 Pregnancy test

It refers to the performance of a rapid pregnancy test in all women of childbearing age who wish to enter the study. By fertile age we understand women who have not had their menopause, defined as 12 months since the last menstrual period in women over 40 years of age; or those who underwent bilateral hysterectomy or oophorectomy. Women of childbearing age with contraceptive methods including bilateral tubal obstruction should be tested for pregnancy. This test will be carried out by the IP or the designated team person according to the instructions of the device delivered by the sponsor. When applicable, the completion, result and date must be registered in the CRF. If you do not apply, you must write down the reason.

6.4.3.11 Lab tests.

The PI will deliver to the subject the order of the studies of BH, QS and PFH, to be carried out in the clinical laboratory designated by the sponsor. The clinical laboratory will deliver to the IP the results for its assessment and registration. The normal parameters to be considered will be the ranges established by the laboratory, Nevertheless the clinical criterion of the PI will prevail in the decision of normality or abnormality of the results.

6.4.4 Measurement time

The measurements of the variables of primary and secondary outcome will be made and evaluated for each visit, according to the following:

Visit scrutiny / Day 0 – X

This visit, by definition, must precede the baseline visit. There is no minimum period to be observed between the scrutiny visit and the baseline, it will depend on having the results of the laboratory tests; notwithstanding, the period between these visits should not exceed 10 days.

Some of these measurements should be complemented with those of the baseline visit and thus meet the eligibility criteria (see Schedule and study diagram), at the discretion of the IP.

1. Laboratory sample taking.
2. Visual ability

3. Intraocular pressure. Índice de confort ocular
4. Evaluation of ocular signs and symptoms
5. Integrity of ocular surface
 - to. Epithelial defects (TF and TVL)
6. TRL
7. Subsequent segment evaluation.
8. Vital signs
9. Evaluation of adverse events

Basal Visit / Day 0.

Some of these measurements will be taken at the screening visit to complete the eligibility criteria (see Schedule and study diagram), at the discretion of the PI, they may be taken to complete the baseline visit data.

1. Visual ability
2. Intraocular pressure.
3. Eye comfort index
4. Evaluation of ocular signs and symptoms
5. Integrity of ocular surface
 - a. Includes stains
6. TRL
7. Subsequent segment evaluation.
8. Vital signs
9. Evaluation of results of laboratory tests
10. Evaluation of adverse events

Visit 1 / Day 3.

It can be done in a period ± 1 day in relation to day 3 of application.

1. Visual ability
2. Intraocular pressure.
3. Evaluation of ocular signs and symptoms
4. Integrity of ocular surface
 - a. Includes stains
5. TRL
6. Vital signs.
7. Evaluation of adverse events.

Final visit/ Day 8.

If the visit can not be made on the 8th, it can be done within a period of up to two days, that is, on the 9th or 10th day. Not before, since the application of the medication will not be completed as dictated the protocol.

1. Visual ability
2. Intraocular pressure.
3. Eye comfort index
4. Evaluation of ocular signs and symptoms
5. Integrity of ocular surface
 - a. Includes stains

6. TRL
7. Subsequent segment evaluation.
8. Vital signs.
9. 9. Evaluation of adverse events.

Security call / Day 12.

It can be done in a period ± 1 day in relation to day 12 of the start of application.

1. Ask about the presence of an adverse event.
2. Evaluation of results of laboratory tests

6.4 Timeline and study diagram

Procedures	Scrutiny	Basal Visit	Visit 1	Final Visit	Call Security
	Day 0 -X	Day 0	Day 3 ± 1	Day 8 a +2	Day 12 ± 1
CI Signature	X				
Clinic history	X				
Ophthalmological clinical history	X				
Laboratory sample taking	X			X	
Laboratory tests review		X			X
Pregnancy test	X			X	
Eligibility criteria	X	X ^a			
Assignment		X			
Delivery of intervention and indication of starting the application the next day day 1.		X			
Return of intervention				X	
Adherence evaluation			X	X	
Adverse events	X	X	X	X	X
Intraocular pressure	X	X ¹	X	X	
Visual ability	X	X ¹	X	X	
TRL	X	X ¹	X	X	
Eye surface integrity	X	X ¹	X	X	
Eye symptoms	X	X ¹	X	X	
posterior segment	X	X ¹		X	
Vital signs	X	X ¹	X	X	
Ocular Comfort Index		X		X	
Daily delivery of the subject		X	X		
Return / Evaluation of the subject's Journal			X	X	
Continuity evaluation of the subject			X		

^a Eligibility criteria will be completed with the review of laboratory tests

¹ These measurements may be taken from the result of the scrutiny visit, if it does not exceed 10 days previous. It is the prerogative of the IP to decide whether to repeat the measurements at the baseline visit.

6.5.1 Procedures to be performed per visit

6.5.1.1 Scrutiny visit

- **Signature of informed consent:** refers to the signing of the written informed consent document. See 10.3 Consent.

- General and ophthalmological clinical history: refers to the technical, clinical and legal document in which the patient's health conditions, medical acts and other procedures performed on the patient are recorded chronologically. It includes the anamnesis and comprehensive ophthalmological exploration that allows to discern the patient's eligibility. If the patient is taken from the established consultation of the study center, he / she will be able to use the existing clinical history, only having to perform an update.
- Taking laboratory samples: see 6.4.3.11 Laboratory tests.
- Pregnancy test: see 6.4.3.11 6.4.3.10 Pregnancy test.
- Eligibility criteria: refers to the review by the IP, where it states that the subject can be included in the study by meeting the inclusion criteria and not meeting the exclusion criteria. See 6.2 Eligibility criteria
- Intraocular pressure: see 6.4.3.5 Intraocular pressure
- Visual ability: see 6.4.3.1 Visual capacity
- TRL: see 6.4.3.9 Rupture time of the tear film
- Integrity of ocular surface: see 6.4.3.3 Integrity of ocular surface:
- Eye symptoms: 6.4.3.8 Ocular symptomatology
- Subsequent segment: see 6.4.3.6 Subsequent segment
- Vital signs: see 6.4.3.7 Vital signs
- Adverse events: see 6.4.3.4 Presence of adverse events6.5.1.2 Visita basal
- Review of laboratory tests: refers to the review and analysis by the IP of the results of the BH, QS and PFH. See 6.4.3.11 Laboratory tests.
- Eligibility criteria: with the laboratory results, the subject's profile will be finalized for inclusion or not.
- Assignment: It refers to determining the intervention that the patient will follow during the study. It will be done according to section 7. Methods. Assignment of the intervention. This assignment will be made at the baseline visit (day 0) and will go along with the indication to start the treatment period the next day (day 1).
- Delivery of intervention: Refers to the delivery of the product under investigation to the patient of the study, by the research center. It will be done according to sections 6.3.1 Managed treatments and 6.3.4.1 Delivery and reception.
- Evaluation of variables: The data of the evaluation of the variables listed below can be taken from the scrutiny visit, as long as it does not exceed 7 days prior to this visit. It is the IP's prerogative to decide whether to use the information from the screening visit or to repeat the evaluations on this visit.
 - Intraocular pressure
 - Visual capacity
 - TRL
 - Integrity of ocular surface
 - Eye symptoms
 - Subsequent segment
 - vital sign
- Eye comfort index: see 6.4.3.2 Eye comfort index
- Delivery of the subject's diary: It refers to the delivery by the IP to the subject, the subject's daily instrument.
- Adverse events: see 6.4.3.4 Presence of adverse events

6.5.1.3 *Visita 1*

- Evaluation of adherence: refers to the assessment made by the IP according to section 6.3.2.1 Procedure to monitor adherence
- Adverse events: see 6.4.3.4 Presence of adverse events
- Intraocular pressure: see 6.4.3.5 Intraocular pressure
- Visual ability: see 6.4.3.1 Visual capacity
- TRL: see 6.4.3.9 Rupture time of the tear film
- Integrity of ocular surface: see 6.4.3.3 Integrity of ocular surface:
- Eye symptoms: 6.4.3.8 Ocular symptomatology
- Vital signs: see 6.4.3.7 Vital signs
- Submission of the subject's diary: see 6.5.1.2 Baseline visit
- Return / daily evaluation of the subject: refers to the delivery of the subject's diary to the IP by the subject. The PI will review the diary to assess its correct filler, evaluate postinstillation symptoms and record applications.
- Continuity assessment of the subject: refers to the determination by the IP and desire of the subject to continue with their participation in the study.

6.5.1.4 *Final Visit*

- Laboratory sample taking: ver6.4.3.11 Laboratory tests
- Pregnancy test: see 6.4.3.10 Pregnancy test
- Return of intervention: see 6.5.1.3 Visit 1.
- Evaluation of adherence: refers to the assessment made by the IP according to section 6.3.2.1 Procedure to monitor adherence
- Adverse events: see 6.4.3.4 Presence of adverse events
- Intraocular pressure: see 6.4.3.5 Intraocular pressure
- Visual ability: see 6.4.3.1 Visual capacity
- TRL: see 6.4.3.9 Rupture time of the tear film
- Integrity of ocular surface: see 6.4.3.3 Integrity of ocular surface:
- Eye symptoms: 6.4.3.8 Ocular symptomatology
- Subsequent segment: see 6.4.3.6 Subsequent segment
- Vital signs: see 6.4.3.7 Vital signs
- Eye comfort index: see 6.4.3.2 Eye comfort index
- Return / daily evaluation of the subject: see 6.5.1.3 Visit 1.

6.5.1.5 *Security call*

- Adverse events: see 6.4.3.4 Presence of adverse events
- Review of laboratory tests: see 6.5.1.2 Baseline visit

6.5.2 *Diagram of the study*

An enrollment time of 30 days is estimated for the total sample.

In addition to safety, the therapeutic adherence will be evaluated and problems related to the procedures will be solved, should they arise.

[figure not shown]

Figure 2. Study diagram

6.6 Sample size

A total size of 30 subjects is estimated, distributed in intervention groups [15 subjects (30 eyes) per group]

6.6.1 Calculation of the sample size

Although there are no references on the calculation of sample size in phase I studies, it was considered pertinent to perform it according to the presentation of adverse events reported by Schwab IR, et al, in a case-control study in 423 subjects with ophthalmic solutions of levofloxacin 0.5 % and ofloxacin 0.3% for 5 days. [22]

The percentage of adverse events that occurred with the preservative-free HS solution was 7.3%, which is why we consider that at least more than 60% of the exposed subjects will not present this rate of adverse events.

The sample size was calculated using the formula for proportions

$$n = \left[(p_1)(p_2) + (p_1)(p_2) \left(\frac{Z_{1-\alpha}}{2} + Z_{1-\beta} \right)^2 \right] / (p_1 - p_2)^2$$

With a statistical confidence of 95% corresponding to the type I error, equal to 1.96, with a power of 80%, corresponding to the type II error, equal 0.84.

According to the previous calculation, the result is 12.5 subjects (13) per group. The total when considering 2 intervention groups is 26 subjects, which was increased by 20% for the probable losses. The total sample size required is 30 subjects. Therefore, each group will consist of 15 subjects, who will provide both eyes for the analysis, so that the total sample to be analyzed will be composed of 60 eyes.

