6.2.3 Elimination criteria

- Withdrawal of the consent letter under information.
- Presentation of a serious adverse event.
- No tolerability or hypersensitivity to any of the compounds used during the tests (fluorescein, green lysine, tetracaine)
- No tolerability or hypersensitivity to any of the investigational drugs.
- Adherence <50% determined by the diary of the subject, of the established dose of the pharmacological intervention in any of the visits.

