7.1 Generation of the allocation sequence

The random numbers will be generated through the online tool:

www.randomization.com

Two strata corresponding to the intervention groups will be used, which will be balanced for a research center. The allocation will be 1: 1.

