Those subjects who comply with an adherence greater than 60% will be included in the statistical analysis to meet the objective of the study. It was considered that from the minimum dose necessary to obtain a pharmacological effect and the presence of adverse events (exposure) is sufficient to fulfill the general objective of the design, according to the pharmacological characteristics of the product under investigation.

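### The 20% increase for losses does not take 26 subjects to 30; it fits only the unrounded 12.5 per group, and 15 per group leaves room for 2 losses (13.3%) before falling below 13

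*Combined protocol and SAP*

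**What the plan says.** Section 6.6.1 gives the calculated size first: "According to the previous calculation, the result is 12.5 subjects (13) per group". It doubles the rounded figure and adds a margin: "The total when considering 2 intervention groups is 26 subjects, which was increased by 20% for the probable losses". It then concludes "The total sample size required is 30 subjects" and splits this equally: "Therefore, each group will consist of 15 subjects, who will provide both eyes for the analysis". The Summary and section 6.6 repeat 30 subjects, 15 per group, and section 7.1 sets equal allocation: "The allocation will be 1: 1".

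Three other places determine who can be lost, and from which analysis:

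- Section 6.2.3 lists reasons for elimination. They are withdrawal of consent, a serious adverse event, intolerance of the study drugs or of the test compounds, and low adherence: "Adherence <50% determined by the diary of the subject".
- Section 8.3.1 sets a higher adherence limit for the analysis: "Those subjects who comply with an adherence greater than 60% will be included in the statistical analysis". Section 8.3.3 restricts the analysis to participants who completed the final visit.
- Section 8.3.1 also says that adverse event reporting counts the eyes of everyone randomised after the baseline visit.

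**The concern.** The sentence names its base (26), its percentage (20%) and its result (30), and the three do not agree. A committee or a reader of the final report would take from it that the trial carries a 20% margin over a requirement of 26. The margin over 26 is smaller than that.

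There is a second difficulty. Raising a number by 20% is not the same as protecting it against a 20% loss, because the loss is taken from the larger, enrolled number. Anyone who compares observed losses with 20% would judge them against a tolerance that 15 per group does not provide. This matters most for the analyses that drop non-completers and low adherers, because there each loss reduces the number analysed.

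**Working it through.** **Inputs, all from section 6.6.1 except the last**

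- Calculated size: 12.5 per group, rounded to 13
- Total before losses: 2 × 13 = 26
- Increase: 20%
- Stated total: 30, or 15 per group
- Allocation 1:1 (section 7.1)

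**1. Reproducing the plan's 30**

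Formula: n × (1 + d), with d = 0.20.

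- From the unrounded size: 12.5 × 1.20 = 15.0 per group, and 2 × 15 = 30. This matches exactly.
- From the base that the text names: 26 × 1.20 = 31.2. Rounded up for two equal groups this is 32, which is 2 more than stated.

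**2. The increase that 30 represents**

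- On 26: (30 − 26) / 26 = 4/26 = 15.4%
- On 25 (2 × 12.5): (30 − 25) / 25 = 20.0%

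**3. The losses that 15 per group can bear**

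- Losses before a group falls below 13: 15 − 13 = 2
- As a share of those enrolled: 2/15 = 13.3%

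**4. A 20% loss among those enrolled**

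- 15 × (1 − 0.20) = 12 per group, or 24 in total. This is below 13 and also below 12.5.

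**5. For comparison, the size that would retain the target after a 20% loss**

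Formula: n / (1 − d).

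- To retain 13: 13 / 0.80 = 16.25, so 17 per group and 34 in total
- To retain 12.5: 12.5 / 0.80 = 15.6, so 16 per group and 32 in total

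**6. Where the losses count**

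| Analysis | Who is included | Effect of losses |
|---|---|---|
| Adverse event reporting (8.3.1) | Eyes of all randomised participants | Denominator stays at 15 subjects per group |
| Analyses limited by 8.3.1 and 8.3.3 | Adherence above 60% and final visit completed | Each loss lowers the number; below 13 after a third loss in a group |

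A subject whose adherence lies between 50% and 60% is not eliminated under section 6.2.3 but is still left out of the analysis under section 8.3.1.

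The 12.5 is taken as given. Section 6.6.1 states 7.3% as one proportion but does not state the second clearly, so the 12.5 cannot be checked from the text. Steps 1 to 6 do not depend on how it was obtained.

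**The case against.** The strongest reply is that nothing is missing. Twenty per cent on the calculated 12.5 gives exactly 15 per group, so the total is right and only its description is loose. Most of this stands. It is the likeliest origin of the 30, although the documents do not say so. It does not rescue the sentence, which rounds to 13, doubles to 26 and names that 26 as the figure increased. Nor does it alter step 4: even on the favourable reading, a 20% loss leaves fewer than 12.5.

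Several stronger readings are tempting but not supported:

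- A reader might infer that the plan contains no loss allowance. It does: 2 subjects per group.
- A reader might infer that the plan promises to keep its size through 20% withdrawals. It describes an increase, not a tolerance, and states no withdrawal rate. For the same reason, a probability that the groups stay at 13 or more would rest on a loss risk that the plan does not give.
- A reader might infer that every analysis shrinks with losses. Section 8.3.1 keeps all randomised participants' eyes in adverse event reporting, and adverse events are the variable on which the size was based.
- A reader might infer from silence that withdrawn subjects will not be replaced. I found no rule either way, and silence is not a rule.

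It is also fair to say that the trial is described as exploratory and that 13 is itself a rounded figure. The documents therefore do not show a specific consequence of analysing 12 rather than 13.

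**Conclusion.** The concern holds in a limited form. The loss sentence in section 6.6.1 is arithmetically wrong as written: its own base and percentage give 31.2 (32 for equal groups), not 30. The gap is 2 subjects. The cushion above the stated 13 is 2 per group, or 13.3% of those enrolled.

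This rests on two assumptions: that 13 per group is the number the plan wants to analyse, and that subjects excluded by the completion and adherence limits count as losses. It concerns only the analyses under those limits. It is an error in a stated design figure that should be corrected. It is not evidence that the trial is too small, and it gives no reason to change the enrolment target, which is stated consistently in the Summary and in sections 6.6 and 6.6.1.

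**What to change.** Keep 30 subjects. In section 6.6.1, replace the sentence on the increase with: *12.5 per group increased by 20% gives 15 per group (30 in total), which allows 2 losses per group (13.3%) while retaining 13.* The sponsor should confirm that this is how the 30 was obtained.

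In the final report, give losses by arm and by reason (elimination, final visit not completed, adherence not above 60%) and compare them with 2 per group.

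The cost is one sentence in the protocol and one table in the report. Enrolment, analyses and decision rules stay as they are. The price is that the stated cushion looks less generous. Applying 20% literally to 26 would mean 32 subjects, and retaining 13 per group after a 20% loss would mean 34; neither is needed to correct the text.

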6.4.1.3 Secondary outcome variables

- Rupture time of the tear film
- Life signs: FC, FR, TAS.
- Posterior segment

6.4.2 Efficacy variables.

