6.4.3 Methods and scales to be used for the measurement of the variables

Variable	Unity	Symbol	Type	Measuring method	Normal value
Age	Years	--	Continuous	Calculation from the date of birth	NA
Gender	Female/ Male	F / M	Nominal	Direct questioning	NA
Adverse events	Number of cases	n	Discreet	Count	NA
Intraocular pressure	Milimeters of mercury	mmHg	Continuous	Goldman's applanation tonometry	11 - 21
Visual ability	Fraction	Snellen	Nominal	Primer	
Tear rupture time	Seconds	s	Continuous	Direct count	> 10
Eye comfort index	points	--	Discreet	Questionnaire	
	Present / Absent	--	Nominal	Comprehensive valuation	Absent
Vital signs					
Heart rate	Beats per minute	lpm	Discreet	Auscultation	60 – 100
Breathing frequency	Breaths per minute	rpm	Discreet	Auscultation	12 – 24
Systemic blood pressure	Milimeters of mercury	mmHg	Continuous	Non-invasive auscultatory measurement	< 120 / 80
Previous segment					
Ocular surface staining	Degrees	--	Discreet	Direct observation with fluorescein and green lysamin stain	Oxford Scale
Ophthalmologic signs and symptoms					

Variable	Unity	Symbol	Type	Measuring method	Normal value
Conjunctival hyperemia	Normal / Very Light / Mild / Moderate / Severe	--	Ordinal	Direct observation. Classification of Efron.	Normal
Chemosis	Present / Away	--	Nominal	Direct observation	Absent
Burning	Severity: Absent, very mild, mild, moderate and severe	--	Nominal	Direct questioning	Absent
Foreign body sensation	Severity: Absent, very mild, mild, moderate and severe	--	Nominal	Direct questioning	Absent
Pruritus	Frequency: At all times, almost at all times, 50% of the time, almost in no time, at any time	--	Nominal	Direct questioning	Absent
Posterior segment					
Macula	Normal / Abnormal	--	Nominal	Direct observation	Normal
Optical disk integrity	Normal / Abnormal	--	Nominal	Direct observation	Normal
Blood count					
Erythrocytes		M/uL	Continuous		
Hemoglobin	Grams over deciliter	g/dL	Continuous		
Hematocrit	Percentage	%	Continuous		
VGM	Femto liters	fL	Continuous		

Variable	Unity	Symbol	Type	Measuring method	Normal value
HCM	picograms	pg	Continuous		
CMHbG	Grams over deciliter	g/dL	Continuous		
Leukocytes	Thousands per liter units	Mil/uL	Continuous		
Platelets	Thousands per liter units	Mil/uL	Continuous		
Myelocytes	Percentage	%	Discreet		
Metamyelocytes	Percentage	%	Discreet		
Bands	Percentage	%	Discreet		
Segmented	Percentage	%	Discreet		
Lymphocytes	Percentage	%	Discreet		
Monocytes	Percentage	%	Discreet		
Eosinophils	Percentage	%	Discreet		

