6.4.3.5 Intraocular pressure

Tonometry is the objective measure of IOP, based primarily on the force required to flatten the cornea or the degree of corneal indentation produced by a fixed force. Goldman's tonometry is based on the Imbert-Fick principle. [26] Tonometry will be performed, after instillation of a drop of topical anesthetic (tetracaine 0.5%), with fluorescein and the use of cobalt blue filter (after evaluation of corneal surface staining). There will be 3 shots, which will be recorded in the clinical file and the average will be registered in the CRF.

6.4.3.6 posterior segment

The evaluation of the posterior segment will be carried out under medication mydriasis (tropicamide 0.8% / phenylephrine 5%), in the slit lamp with an aerial loupe (at the choice of the PI). An integral assessment of the fundus (including optic disk, posterior pole and periphery) will be performed in search of abnormalities that alter the study result. Prior to mydriasis medicamentosa, the evaluation of the iridocorneal angle should be counted, in order to rule out an occludable angle, which is defined as a posterior trabecular mesh visible in less than 90 ° of the angular circumference. [31] [32] The result of the assessment will be recorded in the clinical file. The CRF will record the assessment of the macula and optic nerve as normal, abnormal or abnormality that does not affect.

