8.3 Statistical methodology

8.3.1 Analysis of primary and secondary outcome variables.

The statistical analysis will be carried out by personnel from Sophia Laboratories, S.A. of C.V The statistical program SPSS version 19 (IBM Corporation, Armonk, NY, USA) will be used.

The designated personnel will be blinded to the intervention groups. The coding will be done using consecutive numbers for each intervention group.

The data will be collected and sorted in an excel sheet. Later they will be exported to the platform of the SPSS program. The variables will be categorized according to their nature.

The result of the continuous quantitative variables will be presented in measures of central tendency: media, standard deviation and ranges. **See Table 6.** Scales to be used

The normal distribution of the results will be obtained by the Kolmogorov-Smirnov test.

The statistical analysis of the continuous **quantitative variables** to find significant differences (p) will be the following:

- Intra-group analysis: Wilcoxon rank test.
- Inter-group analysis: Mann-Whitney U test.

The level of difference to consider significance will be of an alpha of 0.05 or less.

The result of nominal and ordinal qualitative variables will be presented in frequencies, proportions and percentages. See table 1 (section 6.4.3).

The statistical analysis to identify significant differences of the **qualitative variables** will be done by creating 2x2 contingency tables and will be done as follows:

- Intra-group difference: McNemar test.
- Difference between groups: test χ^2 (Chi-square) of Pearson.

The level of difference to consider significance will be of an alpha of 0.05 or less.

For the reporting of adverse events all eyes of those participants who were randomly assigned to an intervention group after the baseline visit will be considered. The results will be expressed in number of cases (eyes).

The final report of the results will be shown in tables or graphs, as appropriate.

It will be considered that the investigational drug is safe and tolerable when there are no clinical and statistical differences in all the variables of primary outcome, with respect to its comparators.

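### Both eyes of a subject get the same product but are analysed as 60 separate units, so the IOP comparison rejects about 8.5–14% of the time instead of 5% (assumed between-eye correlation 0.3–0.8)

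*Combined protocol and SAP*

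**What the plan says.** The baseline-visit procedures (6.5.1.2) assign a product to the subject, and 6.3.1.1 and 6.3.1.2 have that product instilled in both eyes. Section 6.6.1 derives the sample size in subjects, ending at 15 per group, and then changes the unit: these are subjects "who will provide both eyes for the analysis, so that the total sample to be analyzed will be composed of 60 eyes". The Summary and 6.6 likewise equate 15 subjects with 30 eyes in each group.

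For continuous variables, 8.3.1 specifies "Inter-group analysis: Mann-Whitney U test". For qualitative variables the comparison is Pearson chi-square, "done by creating 2x2 contingency tables". Both use alpha 0.05. Adverse events are reported as counts of eyes, with no test named. PRO-174 is judged safe and tolerable when "there are no clinical and statistical differences in all the variables of primary outcome, with respect to its comparators".

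The only averaging rule for IOP, in 6.4.3.5, concerns repeat readings: "There will be 3 shots, which will be recorded in the clinical file and the average will be registered in the CRF". No section averages the two eyes, selects one, takes the worse one, or names a paired-eye or clustered method. Section 8.3.2 plans no further analyses unless a specific safety question arises.

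**The concern.** Mann-Whitney and Pearson chi-square take every observation as independent. Two eyes of one person that receive the same product are normally positively correlated, so 60 eyes carry less information than 60 independent units and the p-values come out too small.

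The variables are not equally exposed:

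- **IOP** ("Goldman's applanation tonometry") is the only primary variable that is both measured per eye and typed continuous in 6.4.3. It is clearly affected. So is the secondary variable "Rupture time of the tear film".
- **Visual capacity, hyperemia, chemosis and staining** are also per-eye. Double counting shrinks their p-values, but the chi-square error rate passes 5% only if the finding is not rare. The test for staining is itself unsettled: it is typed discrete, 8.3.1 gives Mann-Whitney to continuous variables, and the Summary gives it to quantitative variables generally.
- **Adverse events** are affected only if they are tested.
- **Comfort index, laboratory tests, vital signs and questioned symptoms** are affected only if entered once per eye.

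At stake is the safety rule in 8.3.1. If the products are truly equal, a falsely significant IOP difference counts against PRO-174. The within-group Wilcoxon and McNemar results are distorted too, but they do not enter that rule.

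**Working it through.** **1. The plan's own sample size is in subjects.** Inputs from 6.6.1: 7.3%, 60%, z = 1.96 and z = 0.84. The section does not label p1 and p2; reading them as 0.073 and 0.60, the mean is 0.3365. The pooled two-proportion formula gives 2 × 0.3365 × 0.6635 × (1.96 + 0.84)² / (0.60 − 0.073)² = 12.6, against the stated 12.5 (13). The plan goes from 26 subjects to 30, and the 60 is 30 × 2 eyes.

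**2. Error rate by formula.** Let rho be the correlation between a subject's eyes. The variance of a group mean over 30 eyes is σ²(1 + rho)/30, but an eye-level test works as if it were σ²/30. The actual rejection rate at nominal two-sided 5% is therefore about 2(1 − Φ(1.96/√(1 + rho))), and 60 eyes are worth 60/(1 + rho) independent units.

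**3. Check by simulation.** Asymptotic two-sided Mann-Whitney, 15 subjects per group, two eyes each, normal data, equal products, 20,000 runs:

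| rho (assumed) | Formula | Simulated, 30 v 30 eyes | Simulated, mean of two eyes | Effective units |
|---|---|---|---|---|
| 0 | 5.0% | 5.1% | 5.2% | 60 |
| 0.3 | 8.6% | 8.5% | 4.9% | 46 |
| 0.5 | 11.0% | 10.9% | 5.2% | 40 |
| 0.8 | 14.4% | 14.4% | 4.9% | 33 |
| 1.0 (bound) | 16.6% | 17.3% | 5.1% | 30 |

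A separate simulation with 40,000 runs gave 8.3%, 10.7% and 14.3% at rho 0.3, 0.5 and 0.8. Ties do not matter: with IOP as the average of three whole-mmHg readings (assumed mean 15.5, SD 2.5), the rates are 8.4%, 11.0% and 14.4%. Taking the higher eye per subject also holds the error at 5.0–5.2%.

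**4. Binary signs.** Exact enumeration, uncorrected Pearson chi-square on eyes, equal products. The documents give no sign rates. The 7.3% is the adverse-event percentage in 6.6.1, whose unit is not stated, and it serves only as one point in the range.

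| Rate per eye (assumed) | rho 0.3 | rho 0.5 | rho 0.8 |
|---|---|---|---|
| 1% | 0.3% | 0.5% | 1.1% |
| 2% | 1.1% | 1.8% | 3.5% |
| 3% | 2.4% | 3.6% | 6.3% |
| 5% | 5.3% | 7.2% | 11.3% |
| 7.3% | 7.7% | 10.1% | 14.9% |

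The error passes 5% only from about 4.8%, 3.8% and 2.6% per eye respectively. For a sign rarer than about 2% there is no material excess.

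**The case against.** **The unit is inferred.** Section 8.3.1 names no unit for IOP; its one explicit eye-level statement concerns adverse-event reporting, and 8.3.1 and 8.3.3 define who is analysed in terms of subjects or participants. This carries some weight, but 6.6.1 says that both eyes enter the analysis and that the analysed sample is 60 eyes. If something else was meant, that text still needs correcting.

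**The size depends on an unknown correlation.** This stands. The objectives in 5.5.2 speak of changes in IOP, and 8.3.1 does not say whether raw values or changes are compared, so the relevant correlation may be that of changes. By the formula, rho 0.1 gives 6.2% and rho 0.2 gives 7.4%. The 8.5% is thus not a floor, but any positive correlation inflates the error.

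**The decision rule has larger sources of false alarm.** Section 6.4.3 lists 16 continuous laboratory variables, also primary, and no multiplicity adjustment is described. If each is tested at 5%, and independence is assumed for illustration, the chance of at least one false signal from these plus a correctly sized IOP test is 1 − 0.95¹⁷ = 58%. With IOP at 8.5%, 10.9% or 14.4% it becomes 60%, 61% or 62%. The overall rule therefore moves little. The reported IOP p-value is still wrong.

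**The error runs against the sponsor's product, in an exploratory trial sized in subjects, under a rule that also asks about clinical difference.** All true. This limits the consequence but does not make the analysis valid.

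**Conclusion.** The concern holds. Followed as written, the plan tests correlated eyes as independent units. For IOP, and in the same way for tear break-up time, the between-group error is about 8.5–14% rather than 5% if the between-eye correlation is 0.3–0.8. That range is an assumption; the excess vanishes at zero correlation and is bounded at about 17% at 1.0. For binary per-eye signs an excess arises only above roughly 2.6–4.8% per eye over the same correlations. Confidence in the defect is high; its exact size cannot be fixed from the documents. It should be corrected, but it does not invalidate the design.

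**What to change.** In 6.6.1 and 8.3.1, state that the unit of inference is the subject (n = 30) and that a subject's two eyes are repeated measurements of one unit. Then:

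- **IOP and tear break-up time:** test the mean of the two eyes or use a model clustered on subject. Show the higher-IOP eye as a supporting summary, so that a one-eyed change is not averaged away.
- **Visual capacity, Efron hyperemia and Oxford grade:** use the worse eye per subject at each visit, with the cut-off for any 2x2 table named in advance.
- **Chemosis and ocular adverse events:** use either eye affected.
- **Comfort index, laboratory tests, vital signs and questioned symptoms:** enter once per subject.
- **Eye-level counts**, including one-eyed changes: keep as descriptive listings.

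Other subject-level summaries would also be valid; what matters is fixing one in advance.

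The cost is wording in two sections and a few lines of code, with no new data. The downside is sensitivity. On subject means, power for IOP at correlation 0.3, 0.5 and 0.8 is about 72%, 67% and 59% for an assumed shift of 0.8 SD, and 89%, 85% and 78% for 1 SD. For a binary sign at an assumed 7.3% of subjects (here a per-subject rate), power against 20%, 30% and 40% is about 14%, 36% and 61%. Chi-square on either eye affected is also conservative: at 7.3% per eye its actual error is 3.2%, 2.7% and 1.9% at correlation 0.3, 0.5 and 0.8.

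Correcting the unit alone would make it easier to declare PRO-174 safe under the current rule. The same amendment must therefore say that a non-significant result with 15 subjects per group is not by itself evidence of safety.
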